### **Censoring Rules for EFS and RFS**

If there are multiple dates associated with one assessment, in order to determine date of progressive or relapsed disease, the assessment date will be set to the first date when the overall response is PD or relapsed disease and the last date otherwise. An EFS or RFS determination is considered adequate if the response is CR, CRI, SD, PD, Relapsed Disease or Refractory.

Table JJCB.6.2 lists censoring rules which will be applied in sensitivity analysis (SA) definitions.

**Table JJCB.6.2. Censoring Rules Sensitivity Analysis Definitions**

Sensitivity Analysis Definition #	Situation	Date of Progression or Censor	Censored / Progressed
SA 1	Patient receives stem cell transplant before relapse, progression or death	Date of stem cell transplant	Censored
SA 2	Relapsed disease, progressive disease or death after $\geq 2$ missed assessments, including blood/bone marrow samples, CT/MRI or PET assessments.	Date of last post baseline assessment before missed assessments or Date of randomization (for EFS) or disease-free state (for RFS) if no other assessment in between	Censored
SA 3	Patient does not have adequate baseline assessment (bone marrow biopsy/aspirate or PET-CT, or CT-MRI)	Date of randomization for EFS analysis Patient not eligible for RFS analysis	Censored
SA 4	Patient is lost to follow-up without relapsed or progressive disease	Date of next scheduled post baseline adequate assessment at or after becoming lost to follow-up	Progressed
SA 5	Patient is lost to follow-up without relapsed or progressive disease	Date of next scheduled post baseline adequate assessment at or after becoming lost to follow-up	Progressed for the treatment arm and censored for the control arm

- Duration of Response (DoR)** DoR for T-ALL is measured from the date of CR, CRi or PR by blood count recovery and bone marrow examination, until the date of relapse. DoR for T-LBL is measured from the time when criteria for response (ie, CR or PR) are met, until the first documentation of relapse or progression. For patients who die without report of relapse, DoR is censored on the date of death, regardless of cause. For a patient with no report of relapse or death by the end of the follow-up data collection, observation is censored at the date of last contact prior to the data inclusion cutoff date.

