10.1.2. Primary Efficacy Measure

For T-ALL patients, assessment of efficacy will be consistent with NCCN guidelines for ALL and Cheson criteria (Cheson et al. 2003). The primary endpoints are defined as follow.

A CR is defined as <5% blasts in an aspirate sample with marrow spicules and with a count of at least 200 nucleated cells, along with peripheral blood levels including platelets $\geq 100 \times 10^9/L$ and absolute neutrophil count (ANC) $\geq 1 \times 10^9/L$ and without circulating blasts.

A CRi is defined as fulfilling all criteria for CR except for residual neutropenia ($<1000/\mu\text{L}$) or thrombocytopenia ($<100,000/\mu\text{L}$). The proportion of patients achieving a CRi is defined as the total number of patients achieving a CRi divided by the total number of patients randomized in that arm.

All previous extramedullary manifestations of disease must be absent (eg, lymphadenopathy, splenomegaly, skin or gum infiltration, testicular masses, CNS involvement). The CR rate is estimated as the total number of patients achieving a CR divided by the total number of patients randomized in that arm.

The ORR (CR and CRi) is the sum of patients achieving a CR and a CRi divided by the total number of patients randomized in that arm.

The Revised Response Criteria for Malignant Lymphoma (Cheson et al. 2007) will be used to assess the efficacy of LY3039478 in T-LBL patients followed by CT scan or MRI.

For patients with T-LBL followed by CT/MRI, the criteria for CR is similar to T-ALL and requires the disappearance of all measurable disease, signs, symptoms, and biochemical changes related to the tumor.

For T-LBL patients assessed by PET-CT, the criteria for CR is as follows: complete metabolic response with the lymph nodes or extralymphatic sites having a score of 1, 2, or 3 with or without a residual mass on the 5-point assessment scale with high physiologic uptake or with activation within spleen or marrow (eg, with chemotherapy or myeloid colony-stimulating factors), uptake may be greater than normal mediastinum and/or liver. In this circumstance, complete metabolic response may be inferred if uptake at sites of initial involvement is no greater than surrounding normal tissue even if the tissue has high physiologic uptake. There can be no new lesions and no evidence of FDG-avid disease in the bone marrow.

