10.1.3.1. T-ALL

For T-ALL: PR rate is defined as a decrease of at least 50% in blast count on the bone marrow aspirate; PR requires all of the hematologic values for a CR but with a decrease of at least 50% in the percentage of blasts to 5% to 25% in the bone marrow aspirate. The proportion of patients achieving a PR is defined as the total number of patients achieving a PR divided by the total number of patients randomized in that arm.

DoR (CR and CRi) is measured from the date of CR or CRi by blood count recovery and bone marrow examination, until the date of relapse. It is measured until the date T-ALL relapse is detected. For patients who die without report of relapse, DoR is censored on the date of death, regardless of cause. For a patient with no report of relapse or death by the end of the follow-up data collection, observation is censored at the date of last contact prior to the data inclusion cutoff date.

Relapse-free survival (RFS) is defined as the timeframe before the reappearance of unequivocal leukemia blast cells in the blood or the bone marrow ($>5\%$), in the CNS (positive cytopspin examination of CSF) or in any other extramedullary site after a CR.

RFS is defined only for patients who achieve CR, and is measured from the date of attaining the leukemia-free state (as defined in Section 10.1.2) until the date of T-ALL relapse or death from

any cause, whichever occurs first. For a patient who is not known to have relapsed or died by the end of study follow-up, observation of RFS is censored at the date of last contact prior to the data inclusion cutoff date.

Event-free survival (EFS) is defined for all patients and measured from the date of entry on study. It is measured until treatment failure, relapse from CR, or death from any cause, whichever occurs first. For a patient with none of these events before the end of study follow-up, observation of EFS is censored at the date of last contact prior to the data inclusion cutoff date. If the patient does not achieve a CR, EFS is defined as the point of treatment failure or death, whichever comes first.

Refractory disease for T-ALL is defined as failure to achieve CR.

Relapsed disease for T-ALL is defined as the reappearance of the blast in the blood or bone marrow (>5%) or any extramedullary site after achievement of a CR.

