### Primary Endpoint:

**Overall Response Rate (ORR)** is defined as the proportion of patients who achieved a best overall response of either complete remission (CR) or incomplete remission (CRI). The ORR (CR and CRI) is the sum of patients achieving a CR or a CRI divided by the total number of patients randomized in that arm.

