### Secondary Endpoints:

- **Partial Response (PR)** is defined as the proportion of patients who achieved a best overall response of partial remission (PR), out of the total number of patients randomized in that arm.
- **Complete Remission (CR)** is defined as the proportion of patients who achieved a best overall response of complete remission (CR), out of the total number of patients randomized in that arm.
- **ORR and PR** is defined as the proportion of patients who achieved a best overall response of either complete remission (CR), incomplete remission (CRI) or partial remission (PR), out of the total number of patients randomized in that arm.

All of the above endpoints (ORR, PR, CR, ORR and PR) will also be calculated for those patients that cross-over in the Phase 2 part of the trial and receive LY3039478 plus dexamethasone after failure of placebo plus dexamethasone.

- **Overall Survival (OS)** is defined for all patients in the trial, and measured from the date of study enrollment to the date of death from any cause. OS duration is measured from the date of randomization to the date of death from any cause in the Phase 2 portion of the study. For each patient who is not known to have died as of the data-inclusion cutoff date for a particular analysis, OS will be censored for that analysis at the date of last contact prior to the

data inclusion cutoff date (contacts considered in the determination of last contact date include AE date, lesion assessment date, visit date, and last known alive date).

- **Relapse Free Survival (RFS)** is defined only for patients who achieve CR/CRI.

For T-ALL, RFS is measured from the date of attaining the leukemia-free state until the date of T-ALL relapse or death from any cause, whichever occurs first. Relapsed disease for T-ALL is defined as the reappearance of the blast in the blood or bone marrow (>5%) or any extramedullary site after achievement of a CR.

For T-LBL, RFS is measured from the time of occurrence of a disease-free state or attainment of a CR to disease recurrence or death as a result of lymphoma or acute toxicity of treatment.

For a patient who is not known to have relapsed or died by the end of study follow-up, observation of RFS is censored at the date of last contact prior to the data inclusion cutoff, at which an adequate assessment was completed, i.e. blood or bone marrow samples, CT-MRI or PET assessment.

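### For T-ALL, CRi counts as remission in ORR, DoR and SAP RFS, but relapse is defined only after a CR, so a CRi responder whose blasts return has no relapse event; the DoR start for CRi is also contradictory

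*SAP*

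**What the plan says.** **Primary endpoint.** SAP 6.11: "The ORR (CR and CRI) is the sum of patients achieving a CR or a CRI divided by the total number of patients randomized", arm by arm. Protocol 10.1.2 sets CRi apart from CR by its blood counts: "A CRi is defined as fulfilling all criteria for CR except for residual neutropenia" or thrombocytopenia.

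**DoR, T-ALL.** SAP 6.11: "DoR for T-ALL is measured from the date of CR, CRi or PR by blood count recovery and bone marrow examination", and it runs until relapse. Protocol 10.1.3.1 uses the same rule without PR: "DoR (CR and CRi) is measured from the date of CR or CRi by blood count recovery and bone marrow examination". Patients who die without a reported relapse are censored at death; those with neither event are censored at last contact. For T-LBL, by contrast, DoR ends at relapse or progression.

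**RFS, T-ALL.** In the SAP, RFS "is defined only for patients who achieve CR/CRI"; Protocol 10.1.3.1 restricts it to patients with CR. The protocol's RFS "is measured from the date of attaining the leukemia-free state (as defined in Section 10.1.2"). The SAP uses the same term for the start, without the cross-reference. In both documents RFS ends at relapse or death from any cause.

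**Relapse, T-ALL.** SAP 6.11 defines it as blasts reappearing in the blood or "bone marrow (>5%) or any extramedullary site after achievement of a CR". Protocol 10.1.3.1 sets the same condition.

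**The concern.** The plan credits CRi as remission and then, for T-ALL, measures how long remission lasts with an event that needs a prior CR. A patient who reaches CRi, never converts to CR and then has blasts return is a responder in ORR but cannot relapse by definition. If the rule is programmed literally, such patients stay relapse-free in DoR until death or last contact, and in RFS until death. The error runs one way: remission looks longer.

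If it is not programmed literally, someone chooses the rule for these patients later, possibly with data in view. The same holds for the DoR start, which ties a CRi date to a recovery that CRi lacks.

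CRi is not a remote case here. Protocol 9.2.2 calls disease-related myelosuppression typical in this setting. Protocol 5.1.6 reports possibly related Grade 4 thrombocytopenia in 3 of 39 patients (7.7%) in the first-in-human study.

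**Working it through.** The point concerns definitions, and the plan states no figure that depends on it, so there is nothing to reproduce first.

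**1. Does CR include CRi?** The documents treat them as separate categories. Protocol 10.1.2 gives separate definitions and separate proportions. The SAP DoR sentence lists CR, CRi and PR side by side. The SAP censoring rules for EFS and RFS list CR and CRI as distinct responses. No sentence says that CR in the relapse definition covers CRi.

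**2. Follow one patient:** T-ALL, best response CRi, blasts then return without a CR in between.

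| Endpoint | Start | Event when blasts return | Result as written |
|---|---|---|---|
| ORR | – | – | Responder |
| DoR (both documents) | CRi date is named, but its dating rule conflicts with CRi | None: needs relapse, which needs a CR | Censored at death or last contact |
| RFS (SAP) | Leukemia-free state | None: same reason | Ends only at death, otherwise censored |
| RFS (protocol) | – | – | Not in the population |
| EFS (both documents) | Study entry | Treatment failure through progressive disease | Event |

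**3. DoR start.** PR requires the CR blood values (Protocol 10.1.3.1), so a start tied to count recovery fits CR and PR. It does not fit CRi, which by definition keeps residual neutropenia or thrombocytopenia.

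**4. RFS start.** The protocol sends the reader to Section 10.1.2 for the leukemia-free state. That section defines CR, CRi, ORR and MRD but never uses this term. RFS and DoR can therefore start on different dates in the same patient.

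**5. Event after PR.** The SAP objective (4.2) and SAP DoR include PR, but T-ALL DoR ends only at relapse. A T-ALL patient whose best response is PR therefore also has no DoR event.

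**6. Size, as an illustration.** From Protocol 12.1 and SAP 5.2: 40 and 20 patients, assumed ORR 40% and 5%.

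- Expected remissions: 40 × 0.40 = 16 on LY3039478; 20 × 0.05 = 1 on placebo.
- Assumed, because the documents do not give it: a CRi share *s* of 25% to 75%. All responders are taken as T-ALL, and CR and CRi patients relapse at the same rate.
- CRi responders with no relapse event: 16 × *s* = 4, 8 or 12 for *s* = 25%, 50%, 75%.
- Counted relapse = true relapse × (1 − *s*):

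| True relapse among CR/CRi | *s* = 25% | *s* = 50% | *s* = 75% |
|---|---|---|---|
| 40% | 30% | 20% | 10% |
| 60% | 45% | 30% | 15% |
| 80% | 60% | 40% | 20% |

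At a true 60%, the standard error with 16 patients is √(0.6 × 0.4 / 16) = 12.2 percentage points. The shift of 15 to 30 points (*s* = 25% to 50%) is about 1.2 to 2.4 standard errors. The formula assumes that CRi patients stay in the risk set to the time point. Those censored earlier pull the estimate back toward that of the CR patients.

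**The case against.** The strongest reply is that context supplies the meaning. CRi is expanded as CR with incomplete blood count recovery, and the SAP defines relapse in the same bullet that admits CR/CRI patients to RFS. The SAP censoring rules for EFS and RFS also date progressive or relapsed disease by the first date on which the response is either, and list both CRI and relapsed disease as adequate determinations. A sensible programmer might then score the CRi patient's relapse. This shows the likely intent, but it does not repair the text. The censoring paragraph only picks a date when one assessment has several. It does not add progression to the RFS events, and it does not address DoR. For T-ALL the DoR sentence stops at relapse, while the T-LBL sentence beside it adds progression.

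Several stronger inferences a reader might draw are not supported:

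- That CRi responders have no DoR start. The sentence names the CRi date; the dating rule contradicts CRi, but the start is not absent.
- That CRi patients fall out of RFS altogether. In the SAP they have a start and a death event; only the protocol excludes them.
- That EFS misses these failures. A patient without CR has an EFS event at treatment failure, which for T-ALL is progressive disease.
- That T-LBL is affected. CRi is defined only for T-ALL, and T-LBL DoR already ends at relapse or progression.

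The objection to the size also stands in part. The CRi share and relapse rate are assumed, some responders will have T-LBL, and PR responders, who belong to SAP DoR, are left out of the 16. With about 1 expected placebo responder, no useful comparison of DoR or RFS between arms is possible either way; what suffers is the test-arm description of durability.

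**Conclusion.** The concern holds for T-ALL in two secondary endpoints. Read as written, a CRi responder whose blasts return has no relapse event in DoR or in SAP RFS. The CRi start date in DoR contradicts the definition of CRi, the protocol's RFS start points to a definition that is not there, and the two documents disagree on who enters RFS.

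The primary ORR is unaffected. EFS is largely unaffected; a small gap may remain because progressive disease (a blast increase of at least 25%) is a different threshold from relapse (blasts above 5%).

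The direction is certain under the literal reading, but the size is not. With an assumed 25% to 50% CRi share among remissions, a true 60% relapse incidence is counted as 45% to 30%. This is an upper bound, since it treats all responders as T-ALL. It describes only the literal reading, with CRi patients kept at risk; if they were instead dropped from DoR, this downward shift would not arise and the result would rest on CR patients only.

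**What to change.** In SAP 6.11 and Protocol 10.1.3.1:

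- Define T-ALL relapse as occurring after achievement of a CR or CRi.
- Start T-ALL DoR on the first date on which all criteria for CR, CRi or PR are met, and delete the words on blood count recovery.
- End T-ALL DoR at relapse or progression, as for T-LBL, so that PR responders also have an event.
- Start T-ALL RFS on the first date on which the CR or CRi criteria are met, in place of the undefined leukemia-free state.
- Align the protocol's RFS population (CR only) with the SAP's (CR/CRi).
- Optionally, for consistency, let EFS count relapse from CR or CRi.

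No new data are needed. Protocol 12.2.1 allows minor clarifications of analysis methods in the SAP before the aggregate database is unblinded; the protocol text should follow so that the two agree. The cost is that reported DoR and RFS may be slightly shorter.

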### ***6.11.1. Primary Outcome and Methodology***

In the Phase 1 portion, the primary outcome of interest is determining the MTD and recommended dose for Phase 2. Efficacy data will be tabulated and listed, no formal hypothesis testing is planned.

In the Phase 2 portion, the primary efficacy endpoint of ORR (CR plus CRi) rate and its exact 95% confidence interval (CI) will be estimated for each treatment arm. The proportion in each treatment arm will be compared using Fisher's exact test. Primary analysis will utilize the ITT analysis set.

Best response will be derived to encompass all tumor assessments from baseline until the earliest objective progression or start of new anticancer therapy. Primary analysis for ORR will be conducted once all enrolled patients have completed 3 cycles of treatment, discontinued treatment, started new anticancer therapy or met criteria for objective progression. Patients who are randomized and do not achieve a CR or CRi will be considered as nonresponders in the primary analysis for ORR.

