8.2. Discussion of Design and Control

A randomized, controlled design is being used in the Phase 2 portion of the study. Randomization minimizes systematic bias in the selection and assignment of patients to study therapy and provides justification for inferential statistical methods to be used on data from this study. Using an appropriate concurrent control arm enables direct statistical estimation of benefits and harms due to study therapy and minimizes bias in the assessment and interpretation of observed treatment effects. To further reduce the potential for bias and improve the power of the analyses, patients will be stratified for differences in factors thought to be associated with clinical outcomes.

Investigational treatment administration in this study is double-blind. Patients, study personnel at investigational sites, and study personnel at Lilly do not have immediate access to treatment assignments for any patients. This design feature minimizes potential bias due to knowledge of treatment assignments during the study.

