**Figure JJCB.5.1. Illustration of study design.**

## 5.2. Determination of Sample Size

Approximately 86 to 92 patients will be enrolled in this multicenter study.

In the Phase 1 portion of the study, the primary objective is to determine the MTD and the recommended dose for Phase 2. Approximately 13 to 16 patients will be enrolled into the adult (Part A), and approximately 13 to 16 patients will be enrolled in the pediatric (Part B) cohorts sequentially and without randomization to dose. The total sample size per cohort will be determined by DLTs.

In the Phase 2 portion of the study, the primary objective of this study is to compare the ORR (CR plus CRi) rate between LY3039478 administered with dexamethasone and placebo administered with dexamethasone, in adult patients with relapsed/refractory T-ALL/T-LBL. Approximately 60 evaluable patients will be randomized to the 2 treatment arms in a 2:1 ratio (40 randomized to LY3039478 and dexamethasone and 20 randomized to placebo and dexamethasone).

Assuming the ORR for the LY3039478 and dexamethasone arm is 40% and the ORR of the placebo and dexamethasone is 5%, the sample size of 60 evaluable patients will give approximately 82% statistical power to detect the difference, using a 2-sided Fisher's test at the significance level of 0.05, with 1 futility interim once the 30th enrolled patient completes the remission status determination.

Patients who are randomized and do not achieve a CR or CRi will be considered as nonresponders in the primary analysis for ORR.

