#### **5.3.2. Phase 2**

Patients who enter the study during the Phase 2 portion will be randomized to receive either LY3039478 in combination with dexamethasone or placebo in combination with dexamethasone. Assignment to treatment groups will be determined by a computer-generated random sequence using an interactive web-response system (IWRS).

A dynamic allocation method, introduced by Pocock and Simon (1975) and extended for unequal treatment group sizes by Han et al. (2009), will be adopted to balance patient assignment between treatment arms, using a probability factor of 0.9, based on the following factors:

- age  $\leq$ 30 years versus  $>$ 30 years
- T-ALL phenotype versus T-LBL, considered as 6 factors, representing the following 5 phenotypes of T-ALL:

TdT+, variable for all of the following: CD1a, CD2, CD3, CD4, CD5, CD7, CD8, CD34

- Pro-T-ALL: cCD3+, CD7+, CD1a-, CD2-, CD4-, CD8-, CD34+/-
- Pre-T-ALL: cCD3+, CD7+, CD1a-, CD2+, CD4-, CD8-, CD34+/-
- Cortical T-ALL: cCD3+, CD7+, CD1a+, CD2+, CD4+, CD8+, CD34-
- Medullary T-ALL: cCD3+, sCD3+, CD7+, CD1a-, CD2+, CD4+or CD8+, CD34-
- ETP T-ALL: Lack of CD1a and CD8 expression, weak CD5 expression with less than 75% positive blasts, and expression of 1 or more of the following myeloid or stem cell markers on at least 25% of lymphoblasts: CD117, CD34, HLA-DR, CD13, CD33, CD11b, and/or CD65

- response to last therapy: refractory/relapse within 1 year of last therapy vs. >1 year

The randomization parameter P will be set to 0.9 to maximize the benefit of the allocation procedure, whilst keeping treatment assignments unpredictable.

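### The primary ORR test ignores the factors used to balance allocation, so it is slightly conservative and forgoes a small amount of power if those factors predict remission

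*SAP*

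**What the plan says.** Protocol 8.2 explains the allocation: "To further reduce the potential for bias and improve the power of the analyses, patients will be stratified for differences in factors". It describes these as likely to be linked to outcome. Protocol 9.3.2 and SAP 5.3.2 implement this as minimization with a probability factor of 0.9 on three factors: age (30 or under v over 30), six categories of T-ALL phenotype or T-LBL, and "response to last therapy: refractory/relapse within 1 year of last therapy vs. >1 year".

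For the primary endpoint, SAP 6.11.1 and protocol 12.2.7 state: "The proportion in each treatment arm will be compared using Fisher's exact test". No stratum or covariate enters. SAP 6.2 allows adjusted efficacy analyses as an option and names no model for ORR. SAP 6.11.3 provides an exploratory stratified log-rank test and an adjusted Cox model, but only for time-to-event endpoints.

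SAP 6.11.2 does prespecify a re-randomization test of the primary outcome. It holds responses and stratification covariates fixed and replays the trial's own allocation about 5000 times. Its status is that of a sensitivity analysis.

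The sample size in SAP 5.2 rests on an unstratified Fisher test, two-sided at the 5% level: "the sample size of 60 evaluable patients will give approximately 82% statistical power to detect the difference".

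**The concern.** Forcing balance on a prognostic factor removes part of the chance variation in the arm difference. A test that ignores the factor still allows for that variation, so its p-values tend to be too large. The secondary survival endpoints are given stratified or adjusted analyses, but the primary endpoint is not, although protocol 8.2 names power as a reason for balancing. With 20 control patients, a few points of power that need no extra data are worth having. A sensitivity analysis cannot replace a primary p-value that falls just above 0.05.

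**Working it through.** **Inputs from the documents.** SAP 5.2 has "40 randomized to LY3039478 and dexamethasone and 20 randomized to placebo and dexamethasone", ORR 40% v 5%, two-sided alpha 0.05. Denominators are fixed at 40 and 20 because "Patients who are randomized and do not achieve a CR or CRi will be considered as nonresponders in the primary analysis for ORR".

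**Assumed inputs.** The documents give no factor prevalences and no effect of any factor on remission. Both are varied below.

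**1. The stated 82%.** The arcsine approximation with continuity correction is

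power = Φ{[arcsin√(p1 − 1/(2n1)) − arcsin√(p0 + 1/(2n0))] × √(4·n1·n0/(n1 + n0)) − 1.96}.

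- p1 − 1/80 = 0.3875 and p0 + 1/40 = 0.075.
- The arcsines are 0.6719 and 0.2774, difference 0.3945.
- √(4·40·20/60) = 7.303, so Φ(2.881 − 1.960) = 82.2%. This reproduces the plan.
- Full enumeration of the two-sided Fisher test gives 87.8%, or 87.7% if the futility rule is treated as binding.

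Both figures are for the unstratified test and borrow nothing from stratification.

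**2. The stratified alternative.** In stratum s, given its total responders, the number on the test arm is hypergeometric under the null. Let T be the sum over strata. Its reference distribution is the convolution of the stratum hypergeometrics. The two-sided p-value sums all outcomes no more probable than the one observed.

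**3. Power with two strata, each exactly 2:1** (20,000 simulated trials per row, Monte Carlo error about 0.2 points). The odds ratio (OR) is that between strata within an arm.

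| ORR | Stratum split | OR | Stratified | Fisher | Gain |
|---|---|---|---|---|---|
| 40% v 5% | 50/50 | 1 | 87.6% | 87.6% | 0.0 |
| 40% v 5% | 50/50 | 3 | 88.7% | 88.2% | 0.5 |
| 40% v 5% | 50/50 | 6 | 90.8% | 88.6% | 2.2 |
| 40% v 5% | 50/50 | 10 | 92.7% | 88.9% | 3.8 |
| 40% v 5% | 75/25 | 6 | 90.8% | 88.2% | 2.6 |
| 40% v 5% | 90/10 | 3 | 88.6% | 88.3% | 0.3 |
| 40% v 5% | 90/10 | 6 | 89.2% | 88.2% | 1.0 |
| 40% v 10% | 50/50 | 6 | 72.5% | 67.6% | 4.9 |

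**4. Power under minimization with P = 0.9** rather than perfect balance. With only response to last therapy as the stratum, the gain at 40% v 5% is about 0 with no effect, 0 to 0.5 at OR 3, and 2.0 at OR 6 (50/50 or 75/25), falling to about 0.5 at 90/10. With control ORR 10% and OR 6 it is about 4 to 5 points, or about 1 at 90/10.

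A second set of runs (6000 trials each, Monte Carlo standard error about 0.4 points) made all three factors prognostic, with log-odds effects of 0, 1 or 2 per factor unit. It assumed age 50/50, response to last therapy 75/25 and phenotype/T-LBL 10/15/25/15/15/20%:

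| Test | No effect | Moderate | Strong |
|---|---|---|---|
| Fisher | 88.0% | 88.3% | 89.9% |
| Exact, 2 strata (last therapy) | 87.8% | 88.5% | 91.0% |
| Exact, 4 strata (last therapy × age) | 86.7% | 87.9% | 91.9% |
| Exact, all 2 × 6 × 2 = 24 cells | 70.9% | 73.6% | 82.5% |

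Relative to Fisher, two strata change power by −0.2, +0.2 and +1.1 points, and four strata by −1.3, −0.4 and +2.0. All 24 cells lose 17.1, 14.7 and 7.4 points.

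**5. Size.** Fisher's exact size without prognostic factors is 1.5%, 2.8% and 3.5% at a common ORR of 5%, 10% and 20%, so discreteness explains most of the conservatism. Under minimization, for no, moderate and strong effects, simulated size is 1.5, 1.2 and 1.0% at ORR 5%; 2.9, 2.4 and 2.0% at 10%; and 3.3, 2.9 and 1.9% at 20%. Under simple randomization with the strong effect it is 1.2, 3.1 and 3.1% at the three rates. Balancing without using the factors therefore costs about 0.2 points of size at 5% and about 1 point at 10 to 20%. The two-stratum test stayed below 5% in every null run.

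**The case against.** The best defence is SAP 6.11.2. A reader might infer that no analysis of the primary endpoint uses the balancing factors. That is not so, because the re-randomization test builds its reference distribution from them. With exactly balanced strata, m total responders and t on the test arm, the crude difference is t/40 − (m − t)/20 = 3t/40 − m/20. It rises with t, so re-randomizing it is essentially the stratified exact test, apart from the two-sided tail rule. What remains is that this analysis is not primary.

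A reader might also infer that the trial falls short of its stated power, or that type I error is at risk. Neither follows. The 82% was set for the unstratified test, and the error is in the conservative direction. Nor is the benefit of balancing wholly lost: with strong factors, Fisher's power was 89.9% under minimization against 88.2% under simple randomization.

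Two further points stand. At the planned 5% control rate the extra conservatism is negligible, since 20 × 5% is about one expected control response. And protocol 7.1 requires refractory disease, or relapse refractory to reinduction, so one level of response to last therapy may hold most patients. That would shrink the gain. Keeping Fisher for a 60-patient trial is therefore defensible. What it lacks is a stated reason, given the power rationale in protocol 8.2.

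**Conclusion.** The point holds as a modest inefficiency. The primary test does not use the factors on which allocation is balanced, and only a sensitivity analysis reflects them. If those factors predict remission, the power forgone at 40% v 5% is about 0 to 2 points for an assumed OR of 1 to 6. It is about 5 points at OR 6 if control ORR is 10%, and clearly less if one stratum holds about 90% of patients. An OR of 10 would give more, but nothing in the documents supports assuming it. All of these sizes rest on assumed prevalences and prognostic effects. The case for change is that a single two-level stratum costs almost nothing if the assumption fails.

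**What to change.** In SAP 6.11.1 and protocol 12.2.7, make the primary test an exact conditional test stratified by the two-level factor response to last therapy, as recorded at randomization. Use the one-year definition in SAP 5.3.2, not the refractory/relapsed split in SAP 6.11.3, and state the two-sided rule. Keep crude Fisher as a sensitivity analysis.

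The alternative is to promote the re-randomization test to primary. SAP 6.11.2 would then have to name one of its two comparisons as the test and fix the number of re-randomizations and the seed. At 5000, the Monte Carlo standard error of a p-value near 0.05 is √(0.05 × 0.95/5000) = 0.003.

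Do not stratify by phenotype, which leaves the cells too sparse. Do not cross with age either, which cost about 1 point of power when the factors were not prognostic. If the sponsor prefers Fisher as primary, it should say why and drop the power rationale in protocol 8.2.

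The cost is wording and a few lines of code, plus a protocol amendment if the primary test counts as a principal feature under protocol 12.2.1. The stratum must be named before unblinding, preferably before the first unblinded Phase 2 interim review. If the factor is not prognostic, power changes by no more than about 0.3 points. The sample size need not change.
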